### 3.3 Study Rationale

In a Phase 2, double-blind, placebo-controlled clinical study the safety and efficacy of VERU-111 in the treatment of SARS-CoV-2 in patients at high risk for ARDS was assessed. Thirty-nine (39) hospitalized patients at high risk for ARDS were randomized to 18 mg of VERU-111 (powder in capsule formulation) or matching placebo. The primary efficacy endpoint for the study was the proportion of patients alive without respiratory failure at Day 15, Day 22, and Day 29. The key secondary endpoints in the study were days on mechanical ventilation, days in intensive care unit (ICU), and proportion of patients discharged from the hospital on Day 15, Day 22, and Day 29. The efficacy conclusions in the Intent-to-Treat (ITT) population from a post-hoc analysis from the Phase 2 study are:

- VERU-111 reduced the proportion of patients who died on study (up to Day 60) from 30% (6/20) in the placebo group to 5% (1/19) in the VERU-111 treated group. This is an approximately 82% reduction in mortality in the VERU-111 treated group.
- VERU-111 reduced the proportion of patients that are treatment failures, i.e. death or respiratory failure from 35.0% in the placebo group to 15.8% in the VERU-111 treated group at Day 15 and from 30.0% in the placebo group to 10.5% in the VERU-111 treated group at Day 29. This represents an approximately 55% reduction in treatment failures at Day 15 and a 65% reduction in treatment failures at Day 29 in the VERU-111 treated group compared to placebo.
- VERU-111 reduced the days on mechanical ventilation from an average of 5.4 days in the placebo group to 1.6 days in the VERU-111 treated group. This represents a 3.4-fold increase in the days on mechanical ventilation in the placebo group compared to the VERU-111 treated group.
- VERU-111 reduced the days in ICU from an average of 9.6 days in the placebo group to 3.0 days in the VERU-111 treated group. This represents a 3.2-fold increase in the days in the ICU in the placebo group compared to the VERU-111 treated group.
- There is an imbalance in the gender distribution between the treatment group such that the placebo group is 85% male (17/20) and the VERU-111 treated group is 53% male (10/19). This imbalance was evaluated as a covariate in the analysis but did not have a significant effect on the conclusions of the study.
- The use of remdesivir and dexamethasone did not have a significant effect on patient outcomes in the study.

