### 6.2 Selection Criteria

#### 6.2.1 Inclusion Criteria

Subjects accepted for this study must:

1. Provide informed consent from the subject or the subject's Legally Authorized Representative (LAR)
2. Aged  $\geq 18$  years
3. Severe Acute Respiratory Syndrome Coronavirus (SARS-CoV-2) infection confirmed by polymerase chain reaction (PCR) test
4. Patients with a WHO Ordinal Scale for Clinical Improvement score of 4 at high risk for ARDS, must have at least one of the known comorbidities for being at high risk, such as, Asthma (moderate to severe), Chronic Lung Disease, Diabetes, Hypertension, Severe Obesity (BMI  $\geq 40$ ), 65 years of age or older, primarily reside in a nursing home or long-term care facility, or immunocompromised and patients with a WHO Ordinal Scale for Clinical Improvement score of 5 or 6 regardless of presence of comorbidities.
5. WHO Ordinal Scale for Clinical Improvement score of 4 (Oxygen by mask or nasal prongs), 5 (Non-invasive ventilation or high-flow oxygen) or 6 (Intubation and mechanical ventilation)
6. Peripheral capillary oxygen saturation ( $\text{SpO}_2$ )  $\leq 94\%$  on room air at screening. If patient is on oxygen therapy at the time of presentation for screening and the  $\text{SpO}_2$  levels were  $\leq 94\%$  prior to introduction to oxygen therapy with proper documentation example EMT notes or ER/ED notes, then the patient is considered to have met this inclusion criterion. If patient is on oxygen therapy at the time of presentation for screening and the  $\text{SpO}_2$  levels prior to introduction to oxygen therapy are unknown, the patient may be considered to have met this inclusion criterion if oxygen therapy is removed and the  $\text{SpO}_2$  levels fall to  $\leq 94\%$ , then the patient is considered to have met this inclusion criterion. However, removal of the oxygen therapy should only be done if it is considered medically reasonable.
7. Subjects must agree to follow doctor's recommendation for oxygen supplementation.
8. Subjects must agree to use acceptable methods of contraception:
  - If female of childbearing potential or a male subject's partner could become pregnant, use acceptable methods of contraception from the time of the first administration of study medication until 6 months following administration of

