### 9.4.1 Primary Endpoint

The primary endpoint for the study will be the proportion of subjects that die on study (up to Day 60).

The number and percentage of deaths will be summarized by treatment group. Mortality rates will be analyzed using a logistic regression model. This model will include treatment as a factor and study site, gender, remdesivir use (No/Yes), dexamethasone use (No/Yes) and WHO Ordinal Scale for Clinical Improvement at baseline as a covariates. The model will be fitted using logit link function. Odds ratios, standard errors, 95% confidence intervals and p-values for the treatment difference will be presented.

The primary analysis will be performed on the ITT analysis set and the ITT data scope regardless of patient's use of rescue medications, protocol violations or investigational product discontinuation consistent with the treatment policy strategy. Every effort will be made to collect vital status up to the end of the study period. Missing data for subjects who are lost to follow up will be imputed using multiple imputation methods. Details for the imputation will be given in the Statistical Analysis Plan (SAP).

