6.6 Baseline Comparability

The comparability of treatment groups with respect to subject demographics and baseline characteristics will be assessed in a descriptive manner, but no formal statistical testing will be performed.

Controlled Quality Management Document		
	Sponsor:	Veru Inc.
	Protocol Number:	V3011902
STATISTICAL ANALYSIS PLAN. PHASE 2-3-4		

Standard continuous or categorical variable summaries will be presented by randomized treatment group for the following variables based on the Safety Analysis Set and mITT Analysis Set:

- Age (years) at Informed Consent
- Age category (<60 years, >=60 years)
- Sex (Female, Male)
- Fertility Status for Women (Childbearing Potential, Post-menopausal, Surgically Sterile)
- Ethnicity (Hispanic or Latino, Not Hispanic or Latino)
- Race (American Indian or Alaska Native, Asian, Black or African American, Native Hawaiian or Other Pacific Islander, White)
- Weight (kg) at Baseline
- Height (cm) at Baseline
- Body Mass Index (BMI) (kg/m²) at Baseline
- WHO Ordinal Scale for Clinical Improvement (descriptive statistics and frequencies for each score category).

The following baseline conditions will be summarized:

- Comorbidities, n (%)
 - Cancer
 - Diabetes
 - Hypertension
 - History of Heart Failure
 - Pneumonia, Renal Issues
 - Respiratory Issues
 - Asthma (subset of Respiratory Issues)
- Oxygen Saturation (SpO₂) (%)
- Creatinine Clearance (mL/min)
- Time from Admission to Randomization (days).

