6.11.1 Primary Efficacy Analysis

The primary endpoint for the study will be the proportion of subjects that die on study (up to Day 60). Responders are subjects who are alive at Day 60.

The number and percentage of deaths will be summarized by treatment group.

Mortality rates will be analyzed using a logistic regression model. The model will include treatment as a factor and gender, study site (or country or region), remdesivir use (No/Yes), dexamethasone use (No/Yes) and WHO Ordinal Scale strata used in randomization as covariates. The model will be fitted using logit link function. Odds ratios, standard errors, 95% confidence intervals and p-values for the treatment difference will be presented.

The primary analysis will be performed on the ITT analysis set and the ITT data scope regardless of patient's use of rescue medications, protocol violations or investigational product discontinuation consistent with the treatment policy strategy. Every effort will be made to collect vital status up to the end of the study period. Missing data for subjects who are lost to follow up will be imputed using multiple imputation methods.

Example SAS code for imputation is as follows:

```
proc mi data=xxx out=imputed1 seed=1234 n impute=50;
class treatment sex site discharge discont remdesivir dexamethasone whostrata
imputedresponse;
fcs logistic(imputedresponse / details likelihood=augment);
var treatment sex site discharge discont remdesivir dexamethasone whostrata
imputedresponse;
run;
```

where IMPUTEDRESPONSE is the response variable to be imputed, TREATMENT is the randomized treatment group (veru/placebo), SEX is sex of the subject (male/female), SITE is study site (if there are issues fitting imputation model then this might be replaced with country or region), DISCHARGE is whether the subject was discharged from the hospital at any time during the study

Controlled Quality Management Document	
	Sponsor: Veru Inc.
	Protocol Number: V3011902
STATISTICAL ANALYSIS PLAN. PHASE 2-3-4	

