(no/yes, populated as ‘no’ for subjects who were not discharged from the hospital prior to withdrawing from the study before Day 60), DISCONT is whether subject discontinued treatment early (no/yes), REMDESIVIR is the use of remdesivir at baseline (no/yes), DEXAMETHASONE is the use of dexamethasone at baseline (no/yes) and WHOSTRATA is the WHO Ordinal Scale strata used in randomization. If the imputation model does not converge when both DISCHARGE and DISCONT variables are included then will be checked if either of them alone can be included in the model. If model converges with DISCHARGE or DISCONT alone but the model with both DISCHARGE and DISCONT does not converge, then imputation model will include only DISCHARGE.

The imputed data sets will be analyzed separately for each imputation using the logistic regression model. If all subjects have the mortality status at Day 60 then the imputation part above will not be used and observed data will be analyzed as such. Example SAS code for logistic regression is as follows:

```
proc logistic data=imputed1 order=internal descending;
by _imputation_;
class imputedresponse treatment sex site remdesivir dexamethasone whostrata
  / param=glm;
model imputedresponse = treatment sex site remdesivir dexamethasone whostrata
  / clodds=both firth;
estimate 'Treatment A vs. Treatment B' treatment 1 -1 / cl e exp;
lsmeans treatment / cl exp diff;
ods output modelanova=imputed_modelanova1
  lsmeans=imputed_lsmeans1
  diffs=imputed_diffs1
  parameterestimates=imputed_parmest1;
run;
```

If there are enough deaths to perform analysis without FIRTH option then it might be dropped out. Note that variable _IMPUTATION_ identifies each of the imputations created by PROC MI.

Finally, results from individual imputations are pooled via Rubin’s rules using PROC MIANALYZE. Example SAS code for pooling log(odds) for each treatment group is as follows:

```
proc mianalyze data=imputed_lsmeans1;
by trt01pn;
modeleffects estimate;
stderr stderr;
ods output parameterestimates=combined_odds1;
```

run;

Example SAS code for pooling log(odds ratio) for each treatment group is as follows:

```
proc mianalyze data=imputed_diffs1;
  modeleffects estimate;
  stderr stderr;
  ods output parameterestimates=combined_diffs1;
run;
```

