6.11.3 Secondary Analyses for the Primary Endpoint

The primary endpoint, mortality rate at Day 60, will also be assessed in the subset of mITT patients and Safety Analysis Set (all treated subjects).

Additionally, similar analysis to primary analysis will be performed in subgroups for region, standard of care, WHO Ordinal Scale at baseline and vaccination status.

To obtain risk differences between treatment groups, the same analysis as described above for primary efficacy analysis will be performed except identity link function will be used. Example SAS code is as follows:

```
proc genmod data=a order=internal;
class treatment sex site remdesivir dexamethasone whostrata;
model response=treatment sex site remdesivir dexamethasone whostrata
  / type3 dist=bin link=identity;
lsmeans treatment / e diff exp cl;
run;
```

Additionally, mortality rates will be summarized using Kaplan-Meier (KM) survival curves and equality of treatment groups will be tested using log-rank test. Hazard ratios will be calculated using the Cox proportional hazards model including terms for treatment, gender, study site (or country or region), remdesivir use (No/Yes), dexamethasone use (No/Yes) and WHO Ordinal Scale strata used in randomization. Any subjects for whom survival status is not available at day 60 will be censored at the day of their last observed assessment or last captured event.

Example SAS code for log-rank test is as follows:

```
proc lifetest data=XXX outsurv=surv1
  plots=survival(atrisk=0 to 60 by 1);
time time*cens(1);
strata treatment;
run;
```

Example SAS code for proportional hazards model is as follows:

```
proc phreg data=XXX;
class treatment sex site remdesivir dexamethasone whostrata;
model time*cens(1)=treatment sex site remdesivir dexamethasone
  whostrata;
```

Controlled Quality Management Document		
	Sponsor:	Veru Inc.
	Protocol Number:	V3011902

```
hazardratio treatment;  
assess ph / resample seed=1234;  
run;
```

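### Age is in no efficacy model: the mortality test stays valid, but it gives up a little efficiency and leaves chance age imbalance uncorrected

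*SAP*

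**What the plan says.** The endpoint in SAP 6.11.1 is binary: "The primary endpoint for the study will be the proportion of subjects that die on study (up to Day 60", closing bracket omitted. The covariates are given as "The model will include treatment as a factor and gender, study site (or country or region), remdesivir use (No/Yes), dexamethasone use (No/Yes", then the WHO stratum used at randomization. The example code agrees: "model imputedresponse = treatment sex site remdesivir dexamethasone whostrata". Protocol 9.4.1 has the same list apart from the country or region alternative and the use of baseline WHO score: "This model will include treatment as a factor and study site, gender, remdesivir use (No/Yes), dexamethasone use (No/Yes".

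The other models follow suit:

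- **Imputation (SAP 6.11.1):** the same covariates plus discharge and treatment discontinuation. No age.
- **Risk difference, identity link (SAP 6.11.3):** the primary covariates. No age.
- **Cox (SAP 6.11.3):** "Hazard ratios will be calculated using the Cox proportional hazards model including terms for treatment, gender, study site (or country or region", then remdesivir, dexamethasone and WHO stratum. No age.
- **Alive without respiratory failure (SAP 6.11.5.1):** refers back to the primary method.
- **Days ANCOVA (SAP 6.11.5.2):** site (or country or region), remdesivir, dexamethasone and WHO stratum. Neither age nor sex, although Protocol 9.5.1.1 includes sex.

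Randomization is stratified by WHO score only (SAP 5). There is no age subgroup (SAP 6.11.3), and the one sensitivity analysis named for the primary endpoint is the tipping point for missing data (SAP 6.11.2). Age enters only as a descriptive baseline variable: "Age (years) at Informed Consent", plus a split at 60 years (SAP 6.6). Protocol 6.2.1 lists "65 years of age or older" among the high-risk conditions for WHO score 4 patients. Neither document says why age was left out.

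**The concern.** The plan treats age as a risk marker at entry and then does not use it in the analysis. Leaving a prognostic baseline covariate out of a logistic model costs some power for the treatment effect. It also means that, if one arm happens to be older, the primary estimate carries that difference. No planned analysis would show whether a mortality result survives adjustment for age.

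The Phase 2 study is a reminder that such imbalances occur: Protocol 3.3 reports 85% versus 53% male in 39 patients, and sex was then examined as a covariate. Sex is now in the Phase 3 primary model; age has no such protection.

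**Working it through.** **Inputs from the documents.** 140 and 70 subjects; 5% versus 25% mortality; smaller effects from the table in Protocol 9.1 (10% versus 25%, 15% versus 30%); two-sided alpha 0.05 overall and 0.0452 at the final analysis (Protocol 9.7.2); Firth logistic regression (SAP 6.11.1).

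**Assumed, because the documents do not give them.** The age effect, the age SD, the WHO mix and the WHO effect on mortality. Age is taken as independent of WHO score.

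**Step 1: the plan's own figures.** SE = sqrt(0.25×0.75/70 + 0.05×0.95/140) = 0.0549. The 95% interval is -0.20 ± 1.96×0.0549 = [-0.308, -0.092], which matches Protocol 9.1. Power at alpha 0.05 is 97.5% (pooled z), 95.4% (unpooled), 96.2% (continuity-corrected) or 97.9% (Fisher). All satisfy the stated lower bound of more than 92%.

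**Step 2: expected deaths.** 140×0.05 + 70×0.25 = 7 + 17.5 = 24.5. At 10% versus 25% it is 14 + 17.5 = 31.5, and at 15% versus 30% it is 21 + 21 = 42.

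**Step 3: chance imbalance.** The SD of the between-arm difference in mean age is sqrt(1/140 + 1/70) = 0.146 age SDs. With an assumed SD of 14 years that is 14×0.1464 = 2.05 years. The effect on the odds of death is OR^(2.05/10): 1.5^0.205 = 1.09 and 2.0^0.205 = 1.15 for odds ratios per decade of 1.5 and 2.0. At the edge of the 95% range (1.96×0.1464 = 0.29 SD), the odds ratio moves by a factor of about 1.12, 1.22 or 1.37 for age odds ratios of 1.5, 2.0 or 3.0 per SD.

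**Step 4: power, effects per SD.** 2,500 trials per scenario, three equal WHO strata (assumed log odds ratio 0.7 per level), alpha 0.05. The Firth model contained treatment and WHO score, without and then with linear age. Power in %, without → with age:

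| Mortality | No age effect | OR 1.5 per SD | OR 2.0 per SD | OR 3.0 per SD |
|---|---|---|---|---|
| 5% vs 25% | 99.0 → 98.8 | 98.7 → 98.8 | 98.6 → 99.0 | 98.3 → 99.5 |
| 10% vs 25% | 81.6 → 81.5 | 82.6 → 83.1 | 80.6 → 83.3 | 80.5 → 85.8 |
| 15% vs 30% | 72.6 → 72.4 | 73.3 → 73.7 | 72.8 → 75.0 | 72.0 → 79.2 |

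The standard error of a single figure near 80% is sqrt(0.8×0.2/2500) = 0.8 points, so differences between columns are partly noise. Each before-and-after pair uses the same simulated trials and is more precise.

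**Step 5: power, effects per decade.** A second simulation used the region version of the primary model, alpha 0.0452, age SD 14, WHO mix 40/45/15% and log-odds 0/1.2/2.0 by stratum. At 10% versus 25%, power rose from 80.2% to 81.9% (OR 1.5 per decade) and from 79.4% to 84.0% (OR 2.0). At 15% versus 30% it rose from 71.9% to 73.1% and from 71.3% to 76.8%. At 5% versus 25% it rose from 98.3% to 98.6%.

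**Step 6: size and imbalance.** Under 25% versus 25%, two-sided rejection was 3.9-5.3% without age and 4.2-5.5% with it. For age odds ratios of 1.5, 2.0 and 3.0 per SD, the unadjusted treatment estimate correlated with age imbalance at 0.12-0.15, 0.17-0.28 and 0.31-0.38. With age in the model the correlation was about 0.

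**The case against.** The case for leaving the model alone has real weight.

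- **Validity.** Randomization protects type I error, and Step 6 confirms it. A reader might infer that the primary test is biased or inflated; it is not. Exposure to imbalance is conditional on the imbalance that occurs, and age will be visible by arm in the tables of SAP 11.1.
- **Size.** A reader might infer that the trial is underpowered for want of age. At the design effect almost nothing is gained. The larger gains need both a smaller treatment effect and a strong age effect. At SD 14, odds ratios of 1.5 and 2.0 per decade are 1.5^1.4 = 1.76 and 2.0^1.4 = 2.64 per SD. At 1.5 per SD the gain is only 0.1 to 0.5 points. Correlation of age with WHO score would shrink the gains further.
- **Textual support.** Age 65 or older is one of eight listed conditions and applies only to WHO score 4; scores 5 and 6 enter regardless. All seven Phase 2 deaths were at score 5 or above (Protocol 3.3).
- **Phase 2.** The protocol says "The use of remdesivir and dexamethasone did not have a significant effect on patient outcomes in the study". A reader might infer that the plan keeps weak covariates and drops a better one. Non-significance in 39 patients cannot show that, and says nothing about age. The sex imbalance concerns a factor already in the primary model.
- **Timing.** SAP version 5.0 was revised during output production, and the interim analysis sits in a separate plan. A late covariate change invites questions about data-driven choice.

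All of this limits the size and the timing of the point. None of it gives a reason for omitting age. With 24.5 expected deaths parameters are scarce, but linear age costs one degree of freedom, far fewer than site, and the planned code already uses Firth penalization.

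**Conclusion.** The point holds as an available improvement to a valid analysis. Age is in no efficacy or imputation model. Including it would cost -0.2 to 0 points of power if age does not matter. If age does matter, it would gain about 1 point or less at 5% versus 25%, about 0.5 to 5 points at 10% versus 25%, and about 0.4 to 7 points at 15% versus 30%. It would also remove from the primary estimate a chance shift of about 9-15% in the odds of death per SD of age imbalance (assumed SD 14 years, odds ratio 1.5-2.0 per decade). These sizes rest on assumed age effects; only their direction follows from general principles.

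A separate inconsistency came out of the check. A reader might infer that every model adjusts for sex. The primary, identity-link and Cox models do, but the SAP days ANCOVA does not, while Protocol 9.5.1.1 does. The two need to be reconciled.

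**What to change.** Before unblinding:

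1. Add age at consent, continuous and linear, to the primary logistic model and its imputation model (SAP 6.11.1, Protocol 9.4.1). The tipping-point code in SAP 6.11.2 should follow, since it is meant to use the same covariates.
2. Add it to the identity-link and Cox models (SAP 6.11.3), the alive-without-respiratory-failure model (SAP 6.11.5.1) and the days ANCOVA (SAP 6.11.5.2), with matching protocol wording.
3. If the identity-link model does not converge with age, obtain the risk difference by standardisation from the logistic model.
4. State the same model in the separate IDMC analysis plan.
5. Reconcile the sex term between SAP 6.11.5.2 and Protocol 9.5.1.1.

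If an interim analysis has already used the current model, keep that model as primary and pre-specify the age-adjusted model as a sensitivity analysis.

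The cost is a SAP amendment, matching protocol wording and one degree of freedom per model. No new data or patients are needed. The SAP's amendment log shows that the site term of this model was already revised before database lock.

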## **8.10 Early Discontinuation of Study Treatment or Early Termination from the Study**

Subjects may prematurely discontinue study treatment for any of the following reasons:

1. Consent withdrawn for further study treatment (specify the reason).
2. Significant and unacceptable adverse event – specify the adverse event leading to discontinuation of study drug
3. Investigator decision (specify the reason), must be approved by the Medical Monitor
4. Non-compliance by subject with protocol requirements, must be approved by the Medical Monitor
5. Lost to follow-up (record the date of last contact)
6. Death (specify the following information)
  - a. Date of death
  - b. Death due to primary disease? Yes or no
  - c. Death due to study drug? Yes or no
  - d. Death due to adverse event? Yes or no
7. Lack of efficacy
8. Study terminated by the Sponsor
9. Other reason (specify the reason) should be approved by the Medical Monitor

The reason for discontinuation of study treatment will be documented for each subject. Subjects who discontinue study drug prematurely will not be replaced. At the time of discontinuation, please fill out the End of Study case report forms (eCRFs) and subject disposition eCRF pages.

Every effort will be made for the patient to complete all study related procedures at Day 15, Day 22, Day 29, Day 45, and Day 60. Every effort will be made to determine patient status (alive or dead) at Day 15, Day 22, Day 29, and Day 60. This determination can be made via telephone contact or public search records.

OF NOTE: For subjects who are terminated from the study prematurely, every effort should be made to have the subject complete all Early Termination Assessments (same as day 22 assessments). The reason for early termination from the study will be documented for each subject. Subjects who are early terminations will not be replaced. At the time of early termination, please fill out the Early Termination and End of Study case report forms.

Every effort should be made to determine patient status (alive or dead) at Day 60. This determination can be made via telephone contact or public search records.

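### The discharge variable in the primary imputation model covers 60 days for subjects with known outcome but stops at withdrawal for lost subjects, which inflates the imputed death risk of untraced in-hospital withdrawals

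*SAP*

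**What the plan says.** The primary endpoint is death up to Day 60, and missing status is multiply imputed by a logistic model (SAP 6.11.1). The predictors are treatment, sex, site, remdesivir, dexamethasone, WHO stratum and two post-randomization variables:

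- DISCHARGE: "DISCHARGE is whether the subject was discharged from the hospital at any time during the study". It is set to 'no' "for subjects who were not discharged from the hospital prior to withdrawing from the study before Day 60".
- DISCONT: "DISCONT is whether subject discontinued treatment early". The SAP does not say whether death on treatment counts.

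If the model converges with one of the two variables but not with both, DISCHARGE is the one kept. If every Day 60 status is known, no imputation is done.

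Protocol 8.10 introduces its list with "Subjects may prematurely discontinue study treatment for any of the following reasons", and death is item 6. The same section asks sites to establish vital status by telephone or from public records.

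SAP 6.11.2 adds a tipping-point grid, run only if the primary result is significant and some status is missing. Its imputation code contains the same two variables. SAP 6.11.3 adds Kaplan-Meier, log-rank and Cox analyses that censor subjects of unknown status. SAP 6.11.5.1 and 6.11.5.6 reuse the primary method for survival without respiratory failure and for earlier mortality.

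**The concern.** Post-randomization predictors are legitimate in multiple imputation if they are measured in the same way for subjects with and without the outcome. DISCHARGE is not. For a subject with known status it is observed over the whole 60 days, so 'no' means one of three things: died in hospital, alive in hospital at Day 60, or withdrew in hospital and was traced later. For an untraced subject it is frozen at withdrawal. The model treats these as one state and passes the death risk of the first group to the second.

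DISCONT adds to this if deaths on treatment are recorded as early discontinuation. The protocol list permits that coding and the SAP does not exclude it.

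At stake is the confirmatory mortality comparison. If more placebo subjects are lost in hospital, the model adds placebo deaths and favours VERU-111. If more are lost on VERU-111, it hides benefit.

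**Working it through.** **The plan's own figures.** Protocol 9.1 assumes 5% mortality on VERU-111 (n = 140) and 25% on placebo (n = 70). The standard error is √(0.05×0.95/140 + 0.25×0.75/70) = 0.0549, so the interval is −0.20 ± 1.96×0.0549 = [−0.308, −0.092], as printed. Pooled normal power is 97.5%, consistent with the stated lower bound of 92%. Neither figure allows for missing status, and the documents give none for the imputation.

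**Step 1: death risk among observed 'no' subjects.** Let m be mortality, d the share of deaths after discharge and s the share of survivors still in hospital at Day 60. Ignoring traced withdrawals,

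h = m(1−d) / [m(1−d) + s(1−m)].

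Only the 5% and 25% values of m come from the protocol; d (0-10%) and s are assumed.

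| s | m = 5% | m = 25% |
|---|---|---|
| 0% | 1.00 | 1.00 |
| 1% | 0.83-0.84 | 0.97 |
| 3% | 0.61-0.64 | 0.91-0.92 |
| 5% | 0.49-0.51 | 0.86-0.87 |
| 10% | 0.32-0.35 | 0.75-0.77 |

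Example: m = 0.05, d = 0.1, s = 0.05 gives 0.045/(0.045 + 0.0475) = 0.49.

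**Step 2: bias in the risk difference (VERU-111 minus placebo).** Let w be the share of an arm with untraced status after in-hospital withdrawal, and p the true death risk of those subjects. Then bias = wV(h−pV) − wP(h−pP).

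- Null, h = 0.75, p = 0.15, 2% VERU-111 and 5% placebo: 0.02×0.60 − 0.05×0.60 = −1.8 points. With 8% placebo: −3.6 points.
- Null, h = 0.9, p = 0.2, 2% and 10%: −5.6 points; reversed, +5.6.
- As above, but p = 0.6: 0.02×0.3 − 0.10×0.3 = −2.4 points.
- Design effect, equal 5%: h cancels and the bias is 0.05×(0.25−0.05) = +1.0 point, against the drug.

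**Step 3: null simulations.** Each scenario is 140:70 with withdrawal unrelated to outcome and no status traced. Error is one-sided in favour of VERU-111 (nominal 2.5%), ignoring the interim look. At 600 trials per scenario the Monte Carlo error is about 1 point. The 15% scenarios were programmed twice, and both results are shown.

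| Mortality, both arms | Withdrawal, VERU-111 / placebo | Imputed death risk | Error, SAP model | Error, fix |
|---|---|---|---|---|
| 15% | 2% / 5% | 74-76% | 5.0-5.5% | 2.0-2.4% |
| 15% | 2% / 8% | 74-76% | 6.8-10% | 2.0-2.4% |
| 20% | 2% / 10% | 92% | 10.0% | 2.2% |

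The fix simulated here imputes from same-arm subjects still in hospital on the withdrawal day. The last row corresponds to about 5.5 missing placebo and 2.3 missing VERU-111 subjects. There the odds ratio is 0.75 with the SAP model and 0.99 with the fix. Varying survivors in hospital at Day 60 over 0-10% and deaths after discharge over 0-20% gives errors of 9.0-13.2%. The SAP model in this row includes DISCONT.

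**Step 4: what removes or reverses it.**

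- Tracing, 2% / 10% scenario: error 5.3% with half of statuses recovered and 2.5% with 90%.
- Smaller imbalance, 1% / 4%, none traced: 4.0%.
- Equal withdrawal under the null: error near 2.5% at 3%, and odds ratio 0.99 at 6%.
- Equal 5% under the design effect: odds ratio 0.21 instead of 0.14, power 95.0% instead of 97.7%.
- 10% VERU-111 and 2% placebo under the design effect: power 74.0% with the SAP model and 97.3% with the fix.

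The 20% and design-effect simulations assume a 45/40/15% WHO mix, withdrawal on Days 1-14, 5% other treatment discontinuation, four regions instead of sites and 10-12 imputations instead of 50. Unless varied, 3% of survivors are in hospital at Day 60 and 10% of deaths follow discharge.

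**The case against.** A reader might infer that in-hospital withdrawals are imputed as near-certain deaths, that both variables are largely set by death, and that the primary result is therefore biased towards the drug. The documents do not support that.

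- **Near-certain is too strong.** Step 1 falls to about 0.5 at 5% mortality with 5% of survivors in hospital at Day 60. Withdrawals traced and found alive also enter the observed 'no' group and lower the risk.
- **DISCONT is only possibly affected.** Nothing states that deaths are coded as discontinuation. Dosing ends by Day 21 or discharge, so later deaths need not set it, and it is dropped if only the joint model fails to converge.
- **Direction and size are open.** No missing-status rate is given, tracing is required, and a double-blind trial gives no particular reason for several-fold heavier placebo loss. If withdrawals truly have high mortality, the bias shrinks.
- **Safeguards exist.** The tipping-point grid runs in the false-positive case. Its extreme cells assign nearly all missing subjects to one outcome and so hardly depend on these variables. The Kaplan-Meier and Cox analyses use neither variable.
- **The choice was prespecified.** The SAP amendment log for version 2.0 records clarification of both variables, apparently at the regulator's request.

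All of this limits the size of the problem, but the asymmetry remains. The tipping point cannot reveal a benefit hidden by heavier loss on VERU-111, because it runs only after significance. The censored analyses are supportive and do not correct the primary estimate. A request for clarification is not an endorsement. Tracing is an intention with no stated yield, and the model matters exactly where tracing fails.

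**Conclusion.** The concern holds in a limited form. As written, DISCHARGE has one meaning for subjects who supply the imputation model and another for subjects who receive imputed values. Untraced in-hospital withdrawals therefore get an inflated death risk, and DISCONT may add to it. That follows from the SAP's definitions.

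The effect on the trial's conclusion is conditional. It requires untraced in-hospital withdrawals, and error in favour of VERU-111 additionally requires heavier loss on placebo. At 2% against 5-8%, that error is about two to four times nominal. The subjects involved are few: at most 0.02×140 = 2.8 on VERU-111 and 0.05×70 = 3.5 to 0.08×70 = 5.6 on placebo. With loss heavier on VERU-111, or equal under a true effect, the error works against the drug. With about 90% of statuses traced it is negligible. These withdrawal and tracing rates are assumptions. The change is worth making because it is inexpensive and acts on the primary estimate; the documents do not show that the result will be biased.

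**What to change.** 1. Replace DISCHARGE with hospital status (in hospital or discharged) on the day of last contact.
2. Impute each lost subject's Day 60 status from same-arm subjects who on that day were alive, under observation and of the same hospital status.
3. Enter the WHO randomization stratum as a model covariate. With about 70 placebo subjects over three strata, matching cells would be too small. Do not use a same-day WHO score: between Day 1 and Day 15 none is scheduled for subjects who stay in hospital (Protocol 8.5 and Appendix B).
4. Define DISCONT as stopping treatment before last contact for a reason other than death, or drop it.
5. Use the same variables in the tipping-point imputation.
6. Report missing vital status by arm, and keep the present model as a sensitivity analysis.

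The cost is SAP wording and reprogramming of one imputation step, with no new visits or data. Because the regulator appears to have asked about these variables, the change should be shared with it.
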